5.5.3 ENROLLMENT, BASELINE, AND/OR RANDOMIZATION

Enrollment officially occurs at the time of providing informed oral consent. See section 5.5.2 for more information about remote processes including enrollment and baseline assessment via telemedicine. For patient and family participants, enrollment occurs prior to completing the baseline assessment and randomization. The date of study enrollment will be tracked and documented for each participant.

Most intervention research in primary care has relied on cluster-randomization at the level of the clinic, which leads to challenges in the interpretation of results due to practice-level imbalances and unmeasured contextual differences.⁶⁰ This study randomizes at the level of person-family dyad, which may lead to between-group spillover and attenuate observed intervention effects. However, as 31 (+/- 5) intervention dyads will be enrolled at each clinic (~4/month), we do not expect widespread changes to standard clinic workflows or practices. We believe the possibility of contamination is low as the intervention consists primarily of one-on-one contact between the interventionist and the person-family dyad, and there are no elements of the intervention that attempt to address clinicians' communication skill. Nevertheless, our analysis plan permits us to assess for the occurrence of contamination by evaluating whether there are changes over time in the control arm related to care processes, such as registration for shared access to the patient portal and advance directive completion. Dyad-level randomization will afford a more nuanced understanding of context and allow examination of group differences by primary care clinic.

Each person-family dyad will be randomized to treatment or control group in a 1:1 ratio using stratified, blocked randomization by doctor with alternating block sizes of 4 and 6 for each clinician.

Randomization will utilize a statistical algorithm within REDCap developed by the project statistician that is unknown to study staff. The randomization module will generate random treatment group assignment of study participants for each participating clinician. Once patient and caregiver informed oral consent (**B4, C2**) have been received by study staff, research staff will initiate the randomization procedure within REDCap. Person-family dyads assigned to the treatment group will receive information about SHARE. Person-family dyads assigned to the control group will receive print materials about the control protocol (See 6.1.1).

Research staff responsible for the randomization protocol after the enrollment visit will be aware of participant assignment status after it occurs. Allocation concealment will be ensured by blinding the PI and research staff conducting follow-up assessments and those responsible for coding study outcomes throughout the study. Only the study statistician, selected unblinded staff (and REDCap administrator),

and members of the data and safety monitoring board (DSMB) will have access to unblinded data before study completion. As randomization occurs at the level of the person-family dyad, clinicians will care for patients in both groups. Clinicians will be blinded to group assignment.

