6.3 MEASURES TO MINIMIZE BIAS

Most intervention research in primary care has relied on cluster-randomization at the level of the clinic, which leads to challenges in the interpretation of results due to practice-level imbalances and unmeasured contextual differences.⁶⁰ This study randomizes at the level of person-family dyad, which may lead to between-group spillover and attenuate observed intervention effects. However, as as many as 31 intervention dyads (+/- 5) will be enrolled at each clinic (~4/month), we do not expect widespread changes to standard clinic workflows or practices. We believe the possibility of contamination is low as the intervention consists primarily of one-on-one contact between the advance care planning facilitator and the person-family dyad, and there are no elements of the intervention that attempt to address clinicians' communication skill. Nevertheless, our analysis plan permits us to assess for the occurrence of contamination by evaluating whether there are changes over time in the control arm related to care processes, such as registration for shared access to the patient portal and advance directive completion.

Dyad-level randomization will afford a more nuanced understanding of context and allow examination of group differences by primary care clinic.

Each person-family dyad will be randomized to treatment or control group in a 1:1 ratio using stratified, blocked randomization by doctor with alternating block sizes of 4 and 6 for each clinician. A statistical program developed by the project statistician and unknown to study staff will be used to prospectively generate random treatment group assignment of study participants for each participating clinician. A set of opaque envelopes will be prepared for each clinician following the results of the statistical program. Upon providing informed oral consent (**B4, C2, D4**) and after completing the baseline enrollment survey (**B6, C3**), research staff will open the next sequentially ordered envelope specifying treatment group by clinician. Person-family dyads assigned to the treatment group will receive information about SHARE. Person-family dyads assigned to the control group will receive print materials about communicating with their doctor.

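### Block sizes of 4 and 6 alternate within each clinician and are printed in the protocol, so a recruiter who knew the order and that clinician's earlier assignments could know up to about 28% of allocations in advance

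*Combined protocol and SAP*

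**What the plan says.** Section 5.5.3 has each dyad "randomized to treatment or control group in a 1:1 ratio", by "stratified, blocked randomization by doctor with alternating block sizes of 4 and 6 for each clinician". Section 6.3 repeats the scheme: "using stratified, blocked randomization by doctor with alternating block sizes of 4 and 6 for each clinician". Neither section says which size comes first.

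On who knows what, section 5.5.3 states: "Research staff responsible for the randomization protocol after the enrollment visit will be aware of participant assignment status after it occurs". Section 6.3 says much the same. Both sections also say that the generating code is hidden. Section 5.5.3: "Randomization will utilize a statistical algorithm within REDCap developed by the project statistician that is unknown to study staff". Section 6.3: "A statistical program developed by the project statistician and unknown to study staff will be used to prospectively generate random treatment group assignment".

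The two sections describe different mechanisms. In 5.5.3 staff start the randomization in a REDCap module. In 6.3 they open the next opaque envelope in a sequence kept for each clinician.

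Section 5.5.2 says that the staff who obtain consent are trained in the study protocol. Where 5.5.3 and 6.3 speak of allocation concealment, they describe blinding of the principal investigator, follow-up assessors and outcome coders. Staff who screen and consent are not named.

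**The concern.** In a permuted block, once one arm has used up its quota, every remaining assignment in that block is determined. This can be exploited only by someone who knows where blocks end. Alternating two sizes fixes the block ends for the whole list as soon as the starting size is known or worked out. Because the list is kept by clinician, the count that has to be tracked is short.

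Randomizing after consent does not remove the problem, because a determined next assignment is known before the next dyad is approached. Section 5.5.1 leaves recruiters some latitude: first calls fall in a window of two to four weeks unless the patient names a date, some patients are contacted again, and clinic staff may refer particular patients. If a recruiter could foresee the next arm, the type of dyad entered could differ between arms. The primary outcome is reported by the caregiver, and masking the assessors at follow-up cannot undo selection at entry.

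**Working it through.** The documents give no predictability figure, so there is none to reproduce.

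**Inputs.** Block sizes of 4 and 6, alternating within clinician, 1:1 (5.5.3 and 6.3). About 248 dyads in total (9.2). The number of clinicians and of dyads per clinician is not given, so the number per clinician, n, is varied as an assumption.

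**1. Certain allocations in one block.** Take a 1:1 block of size 2m, with earlier assignments and the block boundaries known. Enumerating all arrangements (6 for a block of 4, 20 for a block of 6) gives the probability that each position is already determined:

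- Block of 4: 0, 0, 1/3, 1. Sum = 4/3.
- Block of 6: 0, 0, 0, 0.1, 0.4, 1. Sum = 1.5.

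Both agree with the formula 2m/(m+1): 4/3 for m = 2 and 6/4 for m = 3. The shares are 33.3% and 25.0%.

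**2. Complete 4+6 pairs, starting size known.** (4/3 + 3/2)/10 = 2.833/10 = 28.3%.

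**3. Incomplete blocks, starting size known.** Summing the position probabilities over the first n dyads and dividing by n:

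| n per clinician | 4 first | 6 first |
|---|---|---|
| 2 | 0% | 0% |
| 3 | 11.1% | 0% |
| 4 | 33.3% | 2.5% |
| 5 | 26.7% | 10.0% |
| 8 | 17.9% | 18.8% |
| 10 | 28.3% | 28.3% |
| 12 | 23.6% | 23.6% |
| 20 | 28.3% | 28.3% |

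The range is therefore 0% to 33%.

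**4. Less information, and the alternative design.** Simulation with an observer who updates on every earlier assignment for that clinician (6,000 runs per case):

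| What the observer faces | n = 10 | n = 20 | n = 40 |
|---|---|---|---|
| Alternation known, first size unknown | 19% | 21% | 23% |
| Each size drawn at random from 4 and 6 | 6% | 6% | 6% |

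An observer who does not know the sizes is never certain (0%).

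**5. Best-guess hit rate.** With block boundaries known, the expected number of correct guesses in a block of 2m is m + [2^(2m)/C(2m,m) − 1]/2.

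- Block of 4: 2 + (16/6 − 1)/2 = 2.833.
- Block of 6: 3 + (64/20 − 1)/2 = 4.1.
- Together: 6.933/10, about 69%.

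With randomly drawn sizes, simulation gives about 68% to 69%. The change removes certainty; it barely lowers the success of an informed guess.

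**6. Balance.** The largest imbalance within a block is half its size, which is 3 for a block of 6. This is the same whether 4 and 6 alternate or are drawn at random.

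**The case against.** A reader might infer that 28% of this trial's allocations are foreseeable, or that concealment has failed. The documents do not support that. The 28% needs an observer who knows both sizes, the order including the first size, and every earlier assignment for that clinician, and who can influence recruitment. The protocol never states the first size, says twice that the algorithm or program is unknown to study staff, and limits unblinded data to the statistician, selected unblinded staff, the REDCap administrator and the monitoring board. Nothing shows that any selection took place.

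A reader might also call the primary outcome unblinded. That goes too far. Dyads know their group, but under the labels Group A and Group B, without being told which is the intervention (6.3). Follow-up staff are masked (10.1.9.1), survey responses are adjudicated by someone blinded to group (10.1.8), and clinicians are blinded (5.5.3). The outcome is caregiver-reported with partial blinding.

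There are practical obstacles too. Screening of both members, consent and the baseline survey come before randomization in 6.3, which makes it hard to steer a chosen dyad into a predicted slot. Reasons for ineligibility and nonparticipation are recorded (5.5.1). The primary model adjusts for baseline quality of communication (9.4.1), which limits the harm from selection on that score, though not on unmeasured characteristics. Finally, a best guess is right almost as often with random sizes as with alternating ones.

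These points limit the size of the concern but do not remove it. Hiding the program does not hide a rule printed in two sections of a document on which consenting staff are trained. The documents do not say that recruiters and randomizing staff are different people, or that recruiters cannot see earlier assignments. The hit-rate point stands in full, and it is why separating roles matters as much as the block sizes.

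**Conclusion.** The point holds as a preventable design weakness of modest size. The protocol discloses a deterministic order of block sizes within clinician and states no barrier between recruiting staff and earlier assignments. Certain foreknowledge could reach about 28% of allocations over complete 4+6 pairs for a fully informed observer. It is about 19% to 23% if the first size is unknown, 0% to 33% with incomplete blocks, and 0% if the sizes are unknown. The 19% to 23% rests on an assumed 10 to 40 dyads per clinician. How much of this is attainable depends on facts that the documents leave open: the first block size, the dyads per clinician, and whether the same staff recruit and randomize. Random block sizes would bring certainty down to about 6% while leaving the best-guess rate near 68% to 69%.

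**What to change.** 1. In the unused part of the list, have the statistician draw each block size (4 or 6) at random for each clinician. Replace the word alternating in 5.5.3 and 6.3.
2. Move the block sizes to a randomization document held by the statistician, and remove them from anything that recruiting staff hold.
3. Add one sentence saying that staff who screen and consent do not see earlier assignments for that clinician. If the same staff do both jobs, say so and state the safeguard.
4. Reconcile the REDCap module in 5.5.3 with the envelopes in 6.3, so that one mechanism is described.
5. Where blinding is described, call the primary outcome caregiver-reported with partial blinding.

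The cost is regenerating the unused list segments and editing two sections. Sample size, analysis and maximum within-block imbalance do not change. Item 3 may need a change in staffing if recruiters now also randomize.

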Existing asynchronous secure messaging features of the patient portal enable patients and individuals who have shared access to contribute to the electronic health record (e.g., to elaborate on meeting discussions, communicate emerging concerns, or summarize informal family conversations) to inform and stimulate ongoing discussions and documentation. This feature may be leveraged in communications with the interventionist. At the initial meeting the interventionist will clarify ongoing availability for follow-up meetings and seek patient and family input regarding the frequency (e.g., monthly, quarterly) and mode (by phone, via secure electronic messaging through the patient portal) of future “check-in” contacts to assess interest in scheduling future meetings. Subsequent in-person, telephone, or video conference meetings will occur as a result of “check-in” contacts initiated by the interventionist, ad-hoc requests by persons and/or family caregivers, or notable changes in health (e.g., unplanned hospitalization or emergency department visit, or notable change in health or function). SHARE interventionists will be expected to document the occurrence, content, and outcomes of advance care planning conversations after each ACP conversation (E5).

Participants may be asked to complete a brief questionnaire following all interventionist/facilitator meetings about their satisfaction with the conversation and their perception of its importance (E6, E7). Participants will be given the survey via web survey link or as a mailed paper form with a pre-addressed (to the study office or PI’s home address), stamped envelope return to the study team once completed.

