Research staff responsible for the randomization protocol after enrollment will be aware of participant assignment status after it occurs. Allocation concealment will be ensured by blinding the PI and research staff conducting follow-up assessments and those responsible for coding study outcomes throughout the study. Only the study statistician, selected unblinded staff (and REDCap administrator), and members of the data and safety monitoring board (DSMB) will have access to unblinded data before study completion. As randomization occurs at the level of the person-family dyad, clinicians will care for patients in both groups. Clinicians will be blinded to group assignment. Patient-family dyads will have knowledge of group assignment, but no delineation will be made between group assignment indicating which is treatment or control. We will use group naming conventions of (Group A and Group B) to describe group assignment.

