7.2 PARTICIPANT DISCONTINUATION/WITHDRAWAL FROM THE STUDY

We will monitor loss to follow up and discontinuation of participation in the study. Data from screening calls, intervention contacts and participant surveys will be entered into REDCap forms that the data manager will check for completion and accuracy. The data manager will provide semi-monthly reports of missing or inappropriate entries to the PI for clarification and resolution. Standardized electronic data validation checks will be developed within the database constructs using data entry discrepancy flags, programmed query rules, and in certain cases, external rules using SAS code. Monthly reports in aggregate and by study site will be generated summarizing accrual, completeness of follow-up, and study withdrawals. Periodic reports will be generated at the request of the Project Manager or the Principal Investigator. The Data Manager will generate all these reports, working collaboratively with the Biostatistician and study staff. The reason for participant discontinuation or withdrawal from the study will be recorded on the Case Report Form (CRF), tracked in REDCap, and reported to the DSMB. Subjects orally consent and are randomized but do not receive the study intervention may be replaced. Subjects who orally consent and are randomized and receive the study intervention, and subsequently withdraw, or are discontinued from the study will not be replaced.

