9.3 POPULATIONS FOR ANALYSES

The populations for analyses encompass a sample of about 248 person-family dyads who meet eligibility criteria specified in Section 5 of this protocol. The table below summarizes information that will be assessed from patient and family participants.

| 9.3 Table of Assessments | | | | | | | | | | | | |
|---|---|---------------------------------|-------|--------------------------------|------------|-------------|----|----|-----|-----|-----|--|
| Construct | Measure | Items | Range | Validity | Source | Outcome | BL | 6M | 12M | 24M | EOL | |
| Outcomes @ 6 Months, Patient and Family Experience | | | | | | | | | | | | |
| QOC (Primary) | Quality of EOL Communication ^{51,84-87} ; General QOC Subscale and Global (Secondary) | 7 7 | 0-70 | $\alpha=0.79$ $\alpha=0.91$ | P, F | F@6M | X | X | X | X | | |
| ACP (Secondary) | Sudore 4-item ACP engagement μ ^{88,89} | 4 | 0-20 | $\alpha=0.84$ | P, F | F@6M | X | X | X | X | | |
| | Advance Directive Completion ²⁰ | -- | Y/N | -- | EMR | E@6m | | X | X | X | X | |
| Outcomes @ EOL, Quality of Care and Surrogate Decision-Making Experience | | | | | | | | | | | | |
| Quality of EOL (Primary) | Satisfaction w/ Care at the EOL in Dementia ^{51,90} | 10 | 10-40 | $\alpha=0.90$ | F | F@EOL | | | | | X | |
| Surrogate Decision- Making (Secondary) | Decisional conflict scale ⁹¹⁻⁹³ | 16 | 0-100 | $\alpha=0.78$ | F | F@EOL | | | | | X | |
| | Decisional regret – Brehaut ⁹⁴⁻⁹⁶ | 5 | 0-100 | $\alpha=0.81-0.92$ | F | F@EOL | | | | | X | |
| | Anxiety: GAD-7 ^{97,98} | 7 | 0-21 | $\alpha=>0.92$ | F | F@EOL | X | X | X | X | X | |
| EOL care (Secondary) | Burdensome care | | | | EMR/F | EMR@ EOL | | | | | X | |
| Primary Care Interactions and Communication | | | | | | | | | | | | |
| Therapeutic alliance | Human Connection Scale ⁹⁹⁻¹⁰³ | 16 | 16-64 | $\alpha=0.90$ original | F | - | X | X | X | X | | |
| Shared Decision- Making | CollaboRATE μ ¹⁰⁴⁻¹⁰⁷ | 3 | 0-100 | $\alpha=0.89$; 0-9/item | P, F | - | X | X | X | X | | |
| Primary Care Interactions | Frequency/Mode of Contacts ^{29,108,109} (IH) | 5 | -- | Homegrown | F, E | - | X | X | X | X | X | |
| | Use of patient portal | -- | -- | -- | EMR | - | X | X | X | X | X | |
| Implementation, Fidelity/Implementation Processes, Clinic Context (Note: these items will be limited to intervention participants) | | | | | | | | | | | | |
| Acceptability | Acceptability: Recruitment & retention | Consort diagram | | | | - | | | | X | | |

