| Fidelity | Having had 1+ ACP discussion (ACP) | 5 | Y/N | | P, F, I | - | | X | X | X | | |
| | Fidelity to Respecting Choices ^{82,110} | | | | P, F, I, A | - | | X | X | X | | |
| | Registration for Patient Portal | | | | F, E | - | X | X | X | X | | |
| Sustainability | Clinic continues intervention ¹¹¹ | Clinic/Health system leadership | | | | | X | | | | | |
| Patient and Family Characteristics, Caregiving Circumstances | | | | | | | | | | | | |

| | | | | | | | | | | | |
|-----------------------------|---|----|--------|-----------------------------|--------|---|---|---|---|---|--|
| Demographic Factors | Age, Gender, Education, Race/Ethnicity, CG Work ¹¹² , P/CG type of relationship, Health literacy screen ¹¹³ | 14 | | | P/F, F | - | X | | | | |
| | Living arrangement | 1 | | | P/F, F | - | X | X | X | X | |
| Interpersonal relationships | Caregiver/receiver Mutuality (Love, shared activities & values, reciprocity) ^{30,114} | 15 | 0-4 | $\alpha=0.93$ | P, F | - | X | | | | |
| | Family Apgar (family function) ^{115,116} | 5 | 0-20 | $\alpha=0.94$ | P, F | - | X | | | | |
| Health | Modified Telephone Interview for Cognitive Status | 12 | 0-50 | | P | - | X | | | | |
| | Self-rated health, PHQ-2, GAD2 (P) ^{117,118} | 3 | Likert | | P/F, F | - | X | X | X | X | |
| Quality of Life | Quality of Life-AD ¹¹⁹⁻¹²¹ | 13 | 13-52 | $\alpha=0.84$; ICC>0.75 | P/F | - | X | X | X | X | |
| | EuroQOL-5D, ^{122,123} | 6 | | | F | - | X | X | X | X | |
| Caregiving Circumstances | Intensity: Frequency, Type of Help ¹²⁴ | 8 | | Homegrown | F | - | X | X | X | X | |
| | Caregiver self-efficacy ^{125,126} | 4 | 5-20 | Not reported ¹²⁶ | F | - | X | X | X | X | |
| | 12-Item Zarit Burden Int + 1 global ¹²⁷⁻¹²⁹ | 13 | 0-60 | 0.87 | F | - | X | X | X | X | |

Source: P=patient; F=family caregiver; E=EMR; I=interventionist facilitator; A=audiotapes; C=clinic Note: μ =Modified to reflect family perspective.

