10.1.8 QUALITY ASSURANCE AND QUALITY CONTROL

Internal quality management of study conduct, data collection, documentation and completion will proceed as follows:

Oral consent

Study staff will record documentation of the consent process upon participant orally consenting for compliance with GCP, accuracy and completeness. Contextual information such as date and staff member administering consent will be stored electronically via REDCap (See 10.1.9.1 for specifics), and feedback will be provided to ensure proper consenting procedures are followed.

Informed consent

For providers and facilitators, study staff will review documentation of the consenting process upon participant consenting for compliance with GCP, accuracy and completeness. Consent forms will be reviewed upon storage of consent forms in a locked study cabinet or upon upload into OneDrive, and electronically via REDCap when electronic consent is completed (See 10.1.9.1 for specifics), and feedback will be provided to ensure proper consenting procedures are followed.

Metrics and Electronic Data

Study outcomes are primarily participant-reported. Participant preference for mode of data collection for surveys and consent completion will dictate collection of these items either electronically via REDCap links or via paper-pencil forms. All data will be entered and monitored via the REDCap data management system. Quality control metrics for study outcomes include the extent of missingness and item nonresponse. Baseline and follow-up telephone surveys will be audio-recorded. Documented responses in REDCap will be adjudicated by a study team member who did not administer the survey and who is blinded to treatment group.

Protocol Deviations

Protocol deviations will be tracked and documented by research staff via a protocol deviation tracking form. All protocol compliance related events will be reported to the PI immediately, and to the IRB and DSMB at the time of continuing review.

Monitoring and Fidelity

After each advance care planning meeting, interventionists will document their impressions of the meeting content and progress using a Meeting Summary form. The Meeting Summary form includes details about the structure of the meeting (individuals present, location, meeting duration, etc.) as well as a checklist of key fidelity components (**E5**).

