10.1.9 DATA HANDLING AND RECORD KEEPING

10.1.9.1 DATA COLLECTION AND MANAGEMENT RESPONSIBILITIES

To minimize participant burden and disruption to primary care practices, the study team will obtain oral informed consent (**B4, C2, D4**) and conduct a written or electronic baseline survey (**B6, C3**) prior to randomization. Contextual information about how oral consent is obtained will be stored in REDCap. Follow-up and bereavement assessments will be conducted by telephone and web survey via by study staff masked to treatment group (**C7**). Follow-up and bereaved assessments obtained via web survey will be stored in REDCap. Measures of advance directive completion, use of the patient portal, and burdensome care will be extracted from the electronic health record and the Maryland CRISP by study staff masked to treatment group. Data collection will be the responsibility of research staff under the supervision of the research program manager and primary investigator.

All data will be maintained in confidentiality, and confidentiality protections will be included in study staff research training. Data collection will employ standardized data forms. Data from screening calls, intervention contacts and participant surveys will be entered into REDCap forms that the data manager will check for completion and accuracy. The data manager will provide semi-monthly reports of missing or inappropriate entries to the PI for clarification and resolution. Standardized electronic data validation checks will be developed within the database constructs using data entry discrepancy flags, programmed query rules, and in certain cases, external rules using SAS code. Monthly reports in aggregate and by study site will be generated summarizing accrual, completeness of follow-up, and study withdrawals. Periodic reports will be generated at the request of the Project Manager or the Principal Investigator. The Data Manager will generate all these reports, working collaboratively with the Biostatistician and study staff. The study database will comply with current data security standards, provide real-time data entry validation, and provide audit trails documenting changes or corrections of the study data. Data entry or review will require logging into a secure portal with a username and password. The database is hosted by the Johns Hopkins Bloomberg School of Public Health and is HIPAA-compliant.

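### The blinding statements conflict with the plan's own data flows: directly for the PI, and as an unresolved risk for follow-up interviewers and the response adjudicator

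*Combined protocol and SAP*

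**What the plan says.** **Who is blinded.** Section 5.5.3, repeated in 6.3, commits to "blinding the PI and research staff conducting follow-up assessments and those responsible for coding study outcomes throughout the study". Section 6.3 then restricts access to unblinded data before study completion: "Only the study statistician, selected unblinded staff (and REDCap administrator), and members of the data and safety monitoring board (DSMB"). The PI is not on that list. Section 10.1.9.1 has follow-up and bereavement assessments "conducted by telephone and web survey via by study staff masked to treatment group". Section 10.1.8 has recorded survey responses "adjudicated by a study team member who did not administer the survey and who is blinded to treatment group".

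**What reaches the PI.** Sections 7.2 and 10.1.9.1 put screening calls, intervention contacts and participant surveys into one set of REDCap forms, checked by the data manager. Both then state: "The data manager will provide semi-monthly reports of missing or inappropriate entries to the PI for clarification and resolution". Section 6.1.2 describes questionnaires E6 and E7, which may follow facilitator meetings. They can be answered online or on paper, and the paper envelope is addressed to either the study office or the PI's "home address), stamped envelope return to the study team once completed".

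**What may reach the interviewers.** The Section 9.3 table contains an implementation and fidelity block with the note that "these items will be limited to intervention participants". Its row "Having had 1+ ACP discussion (ACP") has five items, lists patient, family and interventionist as sources, and is marked at 6, 12 and 24 months. The Respecting Choices fidelity row also lists patient and family at those times. Under follow-up assessments, Section 8.1 has participants who screen positive for depression or anxiety offered notification of their clinician by the interventionist.

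**The concern.** The primary outcome is caregiver-reported QOC at 6 months, and Section 6.3 accepts that dyads know their own group. In a trial that Section 4.1 calls single-blind, much of the remaining protection lies in masking those who ask the questions, check the answers and resolve doubtful entries. If one person both sees which dyads have facilitator contacts and decides how a questionable QOC entry is settled, that protection is weakened for the entries concerned. The final report would also describe the PI as blinded when the written procedures do not support it. If SHARE-only items were put by masked interviewers before QOC, the interviewer would learn the arm before recording the primary outcome.

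**Working it through.** The point turns mainly on setting sections side by side. Arithmetic enters only to ask what size of bias would matter.

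**1. PI.**
- Facilitator contacts occur only in the SHARE arm (6.1.1, 6.1.2). Controls receive a letter, a brochure and a blank directive.
- Contact entries and survey entries are checked together, and queries on both go to the PI (7.2, 10.1.9.1). No exception is written for contact entries.
- Resolving a query requires knowing which record it concerns, so a query on a contact entry identifies a SHARE dyad.
- The same person receives the queries on survey entries, which include QOC.
- An E6 or E7 form exists only for a dyad that has met a facilitator, so a form posted to the PI's home carries the same information.
- Sections 5.5.3 and 6.3 mention selected unblinded staff, but nowhere are these two tasks assigned to them.

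Followed as written, 7.2 and 10.1.9.1 cannot be squared with 5.5.3 and 6.3.

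**2. Interviewers.**
- Pointing towards a problem: the 9.3 table names patient and family as sources of SHARE-only items at the time points when QOC is collected, and 9.4.2 has study staff collect follow-up by telephone. The Section 8.1 offer refers to an interventionist, whom control dyads do not have.
- Pointing away: the Section 1.3 schedule marks intervention processes only in the ACP and portal-use column and leaves 6, 12 and 24 months blank. The Section 8.1 list of follow-up survey content has no fidelity items. Forms E5, E6/E7 and E10 are possible other sources.
- Not stated: who asks the SHARE-only items, in what order relative to QOC, and who makes the notification offer.

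**3. Adjudicator.** Telephone surveys are audio-recorded and the documented responses are adjudicated (10.1.8). Arm would show only if SHARE-only items are part of that survey, so this limb depends on step 2.

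**4. Numbers.** Section 9.2 gives an unadjusted effect of 0.30 SD, correlation 0.65, 248 dyads, 10% attrition, 222 retained and two-sided alpha 0.05; allocation is 1:1.
- Adjusted effect: 0.30/√(1 − 0.65²) = 0.395 (plan: 0.39).
- Retained: 248 × 0.90 = 223 (plan: 222, or 111 per arm).
- Power at 0.39 with 111 per arm: 82.8% by the normal approximation, 82.5% by noncentral t with 219 df. The plan's claim of more than 80% reproduces.
- Standard error of the adjusted difference, in unadjusted SD units: √(2/111) × √(1 − 0.65²) = 0.1342 × 0.760 = 0.102.

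The documents give no bias figure. As an assumption only, take a true effect of zero and an average shift b favouring SHARE across the whole arm. The two-sided rejection rate is Φ(b/SE − 1.96) + Φ(−b/SE − 1.96):

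| Assumed b (SD) | Share of 0.30 | b/SE | Rejection rate |
|---|---|---|---|
| 0 | 0% | 0 | 5.0% |
| 0.05 | 17% | 0.49 | 7.8% |
| 0.10 | 33% | 0.98 | 16.5% |

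An interviewer effect would act only on telephone responders. If half the arm answered by telephone (also assumed), a shift of 0.10 SD among them averages 0.5 × 0.10 = 0.05 SD over the arm, which is the middle row.

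**The case against.** Several points on the other side are sound.

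- The note in the 9.3 table cannot be a literal survey-branching rule. The same block includes portal registration marked at baseline, before anyone is randomized, and recruitment and retention, although 9.4.1 compares attrition between arms. Portal registration is also tracked in controls (5.5.3, 6.3).
- E6/E7 are optional, can be completed online, and may go to the study office. Section 5.5.1 uses the same pair of return addresses for opt-out postcards, and nothing says that the PI opens the forms.
- The PI does not collect QOC, and query resolution touches only flagged entries. Telephone responses also have a separate blinded adjudicator.
- Operational detail may sit in the Manual of Procedures, which is not among the documents.

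These points reduce the interviewer and adjudicator limbs to a risk. They do not remove the PI conflict, because the query route is stated twice without a firewall.

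A reader might infer that masking fails outright, or that interviewers must know the arm to know which items to ask. The documents do not support either: no text has a masked interviewer asking these items, or asking them before QOC, and no text sends E6/E7 or contact queries to interviewers or the adjudicator. A reader might also add adverse event reporting as a further route to the PI. However, the listing with attribution goes to the DSMB (8.3.5), and the reports that the PI distributes (10.1.6) are not said to show arm.

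**Conclusion.** The point holds as an inconsistency to be resolved. For the PI it is direct: the plan says the PI is blinded throughout, yet gives the PI arm-revealing queries together with outcome-survey queries, and permits SHARE-only forms to be sent to the PI's home. For interviewers it is a plausible risk arising from a table that disagrees with the schedule of activities and the survey content list. For the adjudicator it is conditional on that risk being real.

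The effect on the primary result cannot be sized from the documents. The figure of 111 SHARE dyads at 6 months is an upper bound for the interviewer limb; it assumes that every SHARE caregiver answers by telephone and that SHARE-only items are in the call. The rejection rates of 7.8% and 16.5% follow from assumed shifts and should not be reported as the trial's false-positive rate. They show only that a shift of one-sixth to one-third of the planned effect would matter. Web completion and caregivers' own knowledge of their group, under neutral Group A and B labels (6.3), limit how much assessor unmasking could add. The correction is still worth making because it is specific, inexpensive and can be made without altering endpoint or sample size.

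**What to change.** 1. **PI.** Amend 7.2 and 10.1.9.1 so that queries on intervention contacts go to the selected unblinded staff already named in 5.5.3 and 6.3, and have E6/E7 returned to them. Give the PI outcome queries only, stripped of arm-revealing fields. If the PI must keep the current role, remove the PI from the blinding statement and from resolving outcome queries.
2. **Interviewers.** Reconcile the 9.3 table with Section 1.3 and the follow-up list in 8.1. Either take the SHARE-only items from E5, E6/E7 and E10, or ask identical items of both arms after QOC is complete. Use the same notification wording in both arms for participants who screen positive for depression or anxiety.
3. **Adjudicator.** State in 10.1.8 that the adjudicator sees and hears outcome items only.

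The cost is a change of REDCap permissions, one return address and a small edit to the survey script, using staff roles the plan already has. Some query handling moves from the PI to unblinded staff.
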